Aim 3: Test relative predictive validity of non-specific and specific mechanisms. We will test to what degree changes in non-specific and specific mechanisms predict changes in pain, mood and function, and whether these relationships depend on the treatment received. We will first test Mechanism Change x Treatment interactions to determine whether changes in any candidate mechanisms predict outcomes to a greater degree in one treatment than the other. In the absence of interactions, we will test the degree to which changes in non-specific and specific mechanisms account for unique and shared variance in predicting outcomes.

Aim 4: To address competing causation paths, we will test lagged and cross-lagged effects of early-treatment changes in non-specific and specific mechanisms predicting late-treatment changes in outcomes.

9.2 Sample Size and Randomization

Power consideration for Aim 1:

Based on past findings, we expect that Mindfulness Training (MT) and Spinal Manipulation Therapy (SMT) will have near-equivalent effects on the primary outcome, changes in EO function. We ran power calculations assuming a true difference of 0 between MT and SMT. Please note that we plan to enroll 286 participants to achieve a sample size of 240 completed participants. See below:

Power Analysis of Two-Sample T-Test for Testing Equivalence Using Differences

Power	MT	SMT	Lower	Upper	True Difference	Standard Deviation	Alpha	Beta
	Group	Group						
	Sample Size (N1)	Sample Size (N2)	Lower	Upper	True Difference	Standard Deviation	Alpha	Beta
0.851	120	120	-3.0	3.0	0.0	7.5	0.050	0.149
0.950	120	120	-3.5	3.5	0.0	7.5	0.050	0.050
0.987	120	120	-4.0	4.0	0.0	7.5	0.050	0.013

An equivalence test of means using two one-sided tests on data from a parallel-group design with sample sizes of 120 in the reference group and 120 in the treatment group achieves 85% power at a 5% significance level when the true difference between the means is 0.0, the standard deviation is 7.5, and the equivalence limits are -3.0 and 3.

Power considerations for Aim 2:

We will test effects of MT and SMT on the treatment-specific mechanisms, pre-post treatment changes in mindfulness and spinal stiffness. Per reviewer suggestions and input from our co-I, [name], we expanded the assessment of “mindfulness” to include pain unpleasantness/bothersome ratings and the Multidimensional Assessment of Interoceptive Awareness (MAIA) scale as well as the Five Facets of Mindfulness Questionnaire (FFMQ). We expect MT to produce larger changes in the mindfulness measures than SMT, and for SMT to produce larger changes in spinal stiffness than MT.

Null Hypothesis: Mean1=Mean2. Alternative Hypothesis: Mean1 \neq Mean2

Allocation

Power	N1	N2	Ratio	Alpha	Beta	Mean1	Mean2	S1	S2
0.800	120	120	1.0	0.050	0.200	0.36	0.00	1.00	1.00
0.983	120	120	1.0	0.050	0.017	0.53	0.00	1.00	1.00

Treatment group sample sizes of 120 and 120 will achieve 80% power to detect a difference of Cohen's $d = 0.36$. With a larger effect – $d = .53$ -- at $\alpha=0.05$ we will have 98.3% power to detect a treatment difference.

Power considerations for Aim 3:

The first focus is to determine whether pre-post changes in specific and non-specific mechanisms (e.g., specific: spinal stiffness changes; non-specific: self-efficacy changes) interact with Treatment Condition to predict pre-post changes in DVs (e.g. pain intensity changes). A significant interaction would suggest that pre-post changes in a mechanism factor predicted pre-post changes in a DV **differently** depending on Treatment Condition. In the case of a significant interaction, we will test simple slopes of pre-post mechanism changes for DV changes for each Treatment Condition separately. We do not expect many significant interactions. Thus, we focus our power analyses on detecting increments in R^2 when adding pre-post mechanism change scores into regressions to predict pre-post changes in outcomes.

Multiple Regression Power Analysis

Power	N of independent variables teste	R ² for Independent Variable(s) tested	R ² for Variables controlled
0.74152	1	0.025	0.1
0.81731	1	0.030	0.1
0.79137	1	0.025	0.2
0.86115	1	0.030	0.2
0.84360	1	0.025	0.3
0.90403	1	0.030	0.3

All calculations assume $N=240$ and $\alpha=0.05$. Again note that we expect to recruit 286 subjects to achieve an analyzable sample of 240 completed subjects.

With 10% of variance in pre-post outcome changes accounted by mechanism variables already in the equation, we have 74% power to detect a 2.5% increment in R^2 with the addition of another mechanism variable. This increases to 90% power to detect a 3% increment in R^2 when mechanism variables already in the equation account for 30% of the outcome changes. Note that these power analyses for Aim 3 were based on testing the association between changes in EO function and changes in pain interference.

Treatment Assignment Procedures

Study patients will be randomized to receive either MT or SMT. The order of drug administration for each laboratory session will also be randomized and counterbalanced (placebo vs. naloxone), and double-blinded. All randomization will be carried out using the Proc Plan procedure in SAS version 9.2 (SAS Institute, Cary, NC). This SAS procedure will be used to generate a randomization schedule for each sequential study slot (MT vs. SMT and the order of naloxone/placebo administration in each set of lab visits). Study subjects will be assigned to these previously randomized study slots in the order that they are enrolled, and the previously determined randomization status associated with each slot will determine the study condition each subject is in and the order of drug administration.

The research assistants (RA) at each site who will conduct weekly phone assessments (when applicable) and who will conduct the laboratory pain-induction sessions will be blind to subject treatment condition. The randomization scheme will be implemented by department administrative assistants who will have no other role in the study.

Given the nature of the interventions and that Co-Is Drs. [name] and [name] will be providing intervention-specific oversight (e.g., review of MT and SMT audio- and video-recordings), neither of these Co-Is will be blinded as to intervention assignment. These individuals will not be engaged in review of individual level study data or analysis of study results. The PIs (Drs. [name] and [name]) will be blinded to intervention assignment. Moreover, during routine review of data, PIs and other research staff will also be blinded to participant intervention assignment by hiding from view the columns denoting subject ID and intervention status in the REDCap database.

Double blinding (patient and investigators) as to drug condition for all laboratory sessions will be maintained by the Investigational Pharmacy at each site. Drug blinding will be broken for specific participants as needed in the event of possible safety or side effect issues. This unblinding will be done by the site PIs in conjunction with investigational pharmacists.

Participants will not be blinded to treatment condition: the MT and SMT procedures will be obvious.

Stake Holder	Intervention Group Assignment	Lab Drug Condition	Primary Mechanistic Outcome Measure	Clinical/Functional Outcome Measure
Study Subjects/Patients	Unblinded	Blinded	Unblinded	Unblinded
Instructors/Practitioners	Unblinded	Blinded	Blinded	Blinded
Outcome Assessors	Blinded	Blinded	Unblinded	Unblinded
Statistician	Blinded	Blinded	Unblinded	Unblinded

Principal Investigators	Blinded	Blinded	Blinded	Blinded
-------------------------	---------	---------	---------	---------

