Given existing RCTs,(117-123), we expect MT and SMT to produce similar overall outcomes. As a comparative mechanisms study, analyses will focus primarily on documenting and characterizing mechanism effects. Note that all mechanism and outcome measures will be completed by all participants in both treatments at each assessment point, thus allowing us to test the degree to which mechanisms not specific to a treatment change and account for outcomes. To support the existence of a specific mechanism, analyses would reveal that: 1) putative specific mechanisms (i.e., mindfulness in MT, spinal stiffness in SMT) will show the largest pre-post changes in the relevant treatment condition (e.g., MT mindfulness changes > SMT mindfulness changes); 2) substantial changes in the mechanism will precede and predict substantial subsequent changes in outcomes only in the relevant treatment (e.g., mindfulness changes predict pain interference changes only in MT).

We will also take full advantage of this design and evaluate effects of mechanisms beyond pre- to post-treatment changes in outcomes. To our knowledge, no methodologically rigorous published study has yet examined effects of mechanisms on pre-post changes in concert with effects of mechanisms on maintenance or expansion of gains during follow-up. It may be that the true value of a mechanism may only be revealed through its effects on sustained gains out to 6-mos after treatment. Thus, mechanisms that do not show strong links with pre-post outcome changes may emerge as delayed predictors of 3- and 6-mos outcomes. Only by separating immediate pre-post mechanism effects from longer-term post-treatment mechanism effects can we build on current knowledge regarding the extended value

of C/I interventions for chronic pain.

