Aim 3: Test relative predictive validity of non-specific and specific mechanisms. The primary objective is to test to what degree changes in non-specific and specific mechanisms predict changes in pain, mood and function, and whether these relationships depend on the treatment received. We will first test Mechanism Change x Treatment interactions to determine whether changes in any candidate mechanisms predict outcomes to a greater degree in one treatment than the other. In the absence of interactions, which we expect to be largely the case, we will test the degree to which changes in non-specific and specific mechanisms account for unique and shared variance in predicting outcomes.

Aim 4: To address competing causation paths. The primary objective is to test lagged and cross-lagged effects of early-treatment changes in non-specific and specific mechanisms predicting late-treatment changes in outcomes. Analyses are described in detail above.

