In the absence of interactions, we will use linear mixed effects regression models to test the degree to which changes in non-specific and specific mechanisms account for unique and shared variance in pre-post outcome changes. More specifically, 0-order correlations among mechanism and outcome pre-post change scores will reveal “candidate” mechanisms (i.e., those with significant associations with pre-post outcome changes). We will use a series of hierarchical regressions to examine the degree to which ostensibly different mechanisms account for shared or unique variance in outcome changes. Such analyses will allow us to identify common areas of mechanism overlap (e.g., changes in self-efficacy and pain catastrophizing accounting for much shared variance in pain changes), and mechanism uniqueness (e.g., changes in spinal stiffness accounting for significant unique variance in pain changes even with other mechanism changes controlled).

Aim 4: Address competing causation pathways.

First, we will use an approach and techniques that we have used in previous publications [eg, [name], J.W., Nielson, W.R., Jensen, M.P., Heapy, A., Czlapinski, R., & Kerns, R.D. (2015). Specific and general therapeutic mechanisms in cognitive-behavioral treatment of chronic pain. *Journal of Consulting and Clinical Psychology*. 83, 1-11. PMID: 24979313]. Namely, we will test lagged and cross-

lagged effects using pre- to mid-treatment and mid- to post-treatment epochs. Given that endogenous opioid functioning will be assessed only at pre-and post-treatment, and given that the working alliance and subject expectations for benefit will be assessed only at 3- and 6-weeks, this approach will allow to examine comparable effects across all our specific and non-specific mechanisms. Residual change scores for all mechanism and outcome variables will be computed by regressing mid-treatment on pre-treatment values (i.e., a pre-mid residual change score), and regressing post-treatment on mid-treatment values (i.e., mid-post residual change score). For lagged relationships, regressions will be performed to identify the unique effect of pre-mid mechanism changes on mid-post outcome changes. This will require statistically controlling for the path from pre-mid mechanism change to mid-post mechanism change and pre-mid outcome change to mid-post outcome change. See Figure 1 and 2 below. The red line is the target lagged effect. The two blue lines are the paths to be controlled.

Figure 1

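### Aim 3 shows treatment-specific slopes only after a significant interaction, states no power for that interaction, and treats non-significance as absence

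*Protocol*

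**What the plan says.** Section 3 (Study Design) sets two conditions for a specific mechanism. The first is a larger pre-post change in the relevant arm. The second is that "substantial changes in the mechanism will precede and predict substantial subsequent changes in outcomes only in the relevant treatment", with the example that "mindfulness changes predict pain interference changes only in MT".

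Section 9.1 (Aim 3) puts the matching comparison of MT with SMT first: "We will first test Mechanism Change x Treatment interactions to determine whether changes in any candidate mechanisms predict outcomes to a greater degree". Section 9.2 also calls this the first focus of Aim 3, then says "We do not expect many significant interactions. Thus, we focus our power analyses on detecting increments in" R². The power table that follows uses N = 240, both arms together. It was built on change in EO function, which the protocol classes as a non-specific mechanism.

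Arm-specific estimates are conditional: "In the case of a significant interaction, we will test simple slopes of pre-post mechanism changes for DV changes for each Treatment Condition separately". Section 9.6 likewise interprets the effect within each group only if the difference is significant. The other branch reads "In the absence of interactions, we will use linear mixed effects regression models". Those models ask how far the mechanism changes overlap or contribute separately to outcome change, with no split by treatment. Section 9.5 says this branch is expected to be the usual one. No interaction effect size, interaction power or bound for calling the two slopes similar appears in these sections.

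**The concern.** Whether a mechanism predicts outcome in one arm and not in the other is a question about the difference between two slopes. The plan answers it with a significance test of unstated power, and a non-significant result removes the arm-specific estimates that a reader would need to judge the Section 3 condition. Non-significance is described as absence, although Aim 1 of the same protocol uses explicit equivalence limits when it wants to claim similarity.

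The risk is that a mechanism which does work in one treatment only is not recognised as such. It may then appear as a significant predictor across both arms, or it may drop out, because Section 9.6 selects candidate mechanisms by significant zero-order correlations.

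**Working it through.** **1. The stated table.** Inputs from Section 9.2: N = 240, alpha = 0.05, one tested variable, R² increment 0.025 or 0.030, controlled R² 0.1, 0.2 or 0.3. With f² = R²(tested) / (1 − R²(controlled) − R²(tested)), λ = 240 × f², and a noncentral F on 1 and 237 df (one controlled variable):

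- First row: f² = 0.025/0.875 = 0.0286, λ = 6.86, power 0.74152.
- Last row: f² = 0.030/0.670 = 0.0448, λ = 10.75, power 0.90403.

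All six rows reproduce to five decimals. The table is correct for an increment over both arms together. It does not address the interaction.

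**2. Interaction power for a one-arm effect.** Assume 120 per arm, equal mechanism variance in the arms, own-arm slope ρ and zero slope in the other arm, all standardised. With arms coded ±½, the pooled slope is ρ/2 and explains ρ²/4 of the variance. The interaction explains a further ρ²/4, so together they explain ρ²/2. Then f² = (ρ²/4) / (1 − R²(controlled) − ρ²/2), λ = 240 × f², on 1 and 235 df.

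Example: own-arm R² 0.025 and controlled R² 0.1 give f² = 0.00625/0.8875 = 0.00704, λ = 1.69 and power 0.254.

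| Own-arm R² (assumed) | Power, controlled R² 0.1 | Power, controlled R² 0.3 |
|---|---|---|
| 0.025 | 0.254 | 0.313 |
| 0.03 | 0.295 | 0.365 |
| 0.05 | 0.454 | 0.556 |
| 0.09 | 0.706 | 0.816 |
| 0.10 | 0.754 | 0.857 |
| 0.12 | 0.830 | 0.916 |

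Power of 80% needs own-arm R² of 0.111 (r = .33) at controlled R² 0.1, or 0.087 (r = .29) at controlled R² 0.3. At own-arm R² of 0.03, 80% power would need about 929 or 719 completers respectively, against 240 planned.

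**3. The other reading of 2.5-3%.** If a one-arm effect produced a pooled increment of 0.025 or 0.030, then ρ²/4 equals that value and own-arm R² is 0.10 or 0.12. Interaction power is then 0.754 and 0.830 at controlled R² 0.1, close to the tabulated 0.742 and 0.817. At controlled R² 0.3 it is 0.857 and 0.916, against 0.844 and 0.904.

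**4. What a missed interaction leads to.** Simulation with 120 per arm, zero slope in the other arm, no controlled variables and 4,000 runs per case. The pooled slope is adjusted for treatment.

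| Own-arm r | Interaction significant | Missed, pooled slope significant | Neither |
|---|---|---|---|
| .173 | 27.6% | 19.2% | 53.2% |
| .20 | 34.5% | 23.3% | 42.2% |
| .30 | 63.3% | 23.7% | 13.1% |
| .346 | 76.9% | 18.4% | 4.7% |

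The last column is 100% minus the other two, before rounding.

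**The case against.** The strongest reply has five parts.

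- **Frequency.** A reader might infer that a truly specific mechanism will usually be reported as shared. The figures do not support that. A missed interaction with a significant pooled slope occurs in about 18-24% of runs at r of .17 to .35. At r = .17 the most common result is neither effect, and at r = .30 and above the interaction is found more often than missed. Nor does the protocol say that a non-significant interaction will be reported as a mechanism common to both treatments: in Section 9.6 shared variance means overlap among mechanisms. This part of the reply stands.
- **Effect size.** A reader might take r of about .17 in one arm as the size Aim 3 is powered for. The 2.5-3% in Section 9.2 is an increment over both arms, and moving it into one arm is an assumption. On the reading in step 3 the interaction is powered about as well as the table. This stands too, so only a range can be given.
- **Aim 4.** The Section 3 condition also requires mechanism change to come before outcome change, which a concurrent pre-post interaction cannot test. The weekly analysis in Section 9.6 asks whether lagged effects differ between MT and SMT and is not conditional on the Aim 3 interaction. That softens the point. It does not remove it, since Aim 4 has no power figure and leaves the Aim 3 rule in place.
- **Expectation.** Not expecting many interactions leaves room for the two specific mechanisms. True, but those are the cases on which the Section 3 condition depends, and they have no power figure.
- **Scope.** Aim 3 is a secondary objective, the larger-change condition is powered under Aim 2, and reporting detail may belong to an analysis plan that is not shown. The protocol itself, however, fixes the criterion, the conditional slopes and the power basis, and these do not fit together.

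**Conclusion.** The point holds in a limited form. The Aim 3 rule can hide the evidence that the Section 3 condition calls for, and it treats a non-significant interaction as absent without any stated power or bound.

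Its size depends on an own-arm effect that the protocol does not give. With no effect in the other arm and controlled R² of 0.1 to 0.3, interaction power is about 25-37% at own-arm R² of 0.025-0.03 and 45-56% at 0.05, and it reaches 80% only at about 0.09-0.11. It is not low at every effect size, and the stated power table is not wrong. That both arms are modelled together is read from N = 240 and the lack of a split by treatment; the protocol does not use the word pooled. The calculation assumes equal arms and equal mechanism variance. If the other arm's slope is weaker but not zero (r = .3 against .1), power is 39-48%.

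**What to change.** For mindfulness and spinal stiffness predicting pain interference, report the MT slope, the SMT slope, their difference and its 95% CI whatever the interaction p-value. Base the statement on specificity on that difference together with the Aim 4 lagged comparison by arm. In Sections 9.1, 9.2, 9.5 and 9.6, replace the wording about absence of interactions so that a non-significant result is not read as equal slopes. Add to Section 9.2 the interaction power over a range of own-arm effects, with the assumption about the other arm stated.

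The cost is wording and a less favourable stated power. No new data or participants are needed.

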9.3 Definition of Populations

The ITT (intent to treat) sample will be all subjects who complete baseline measures. The “per protocol” sample (i.e., “treatment completers”) will be those subjects who complete at least 6 of the 8 treatment sessions.

9.4 Interim Analyses and Stopping Rules

We do not plan to conduct interim analyses.

Findings that would trigger a safety review are two or more occurrences of a particular type of SAE, severe AEs/reactions, or increased frequency of events. The site PIs would present them to the IMC statistician to review the events by group to determine whether there are statistical as well as clinical concerns. The statistician reports his findings to a closed session of the IMC and/or NCCIH. The findings are used to determine what steps will be taken.

9.5 Outcomes

In Aims 1 and 2, our goal is to test the degree to which MT and SMT change specific and non-specific mechanisms. Thus, we will assess pre-post treatment changes in mindfulness and spinal stiffness (specific mechanisms), and in endogenous opioid (EO) function, CPM, pain-related cognition and therapy factors (non-specific mechanisms). For the sake of analyses for Aims 1 and 2, changes in these variables are “outcomes.” The primary mechanism outcome is change in EO function.

In Aim 3, our goal is to determine the degree to which treatment-induced changes in mechanisms are related to treatment-induced changes in the pain, mood and function dependent variables. Prior to the multiple variate analyses, we will determine the degree to which MT and SMT affect pre-post changes in the primary dependent variable, “pain interference” and in secondary dependent variables (mood and function). Our primary goal in this project is to ascertain the degree to which MT and SMT alter putative mechanisms of action. Change in pain interference is the primary dependent variable, reflecting treatment effects, which will be predicted by change in mechanism factors.

Aim 1: Test effects of 2 treatments on non-specific mechanisms. The primary objective is to test to what degree MT and SMT produce changes in the 3 categories of non-specific mechanisms. The primary endpoints depend on the particular mechanism being examined: endogenous opioid function, conditioned pain modulation, pain-related cognition, and therapy factors. Analyses are described in detail below.

Aim 2: Test effects of 2 treatments on specific mechanisms. The primary objective is to test to what degree MT and SMT produce changes in treatment-specific mechanisms. The primary endpoints depend on the particular mechanism being examined: changes in mindfulness and spinal stiffness. Analyses are described in detail below.

Aim 3: Test relative predictive validity of non-specific and specific mechanisms. The primary objective is to test to what degree changes in non-specific and specific mechanisms predict changes in pain, mood and function, and whether these relationships depend on the treatment received. We will first test Mechanism Change x Treatment interactions to determine whether changes in any candidate mechanisms predict outcomes to a greater degree in one treatment than the other. In the absence of interactions, which we expect to be largely the case, we will test the degree to which changes in non-specific and specific mechanisms account for unique and shared variance in predicting outcomes.

Aim 4: To address competing causation paths. The primary objective is to test lagged and cross-lagged effects of early-treatment changes in non-specific and specific mechanisms predicting late-treatment changes in outcomes. Analyses are described in detail above.

